## **2.11 Concomitant illness and medication**

### **2.11.1 Concomitant illness**

Details of concomitant illness of relevance to the inclusion and exclusion criteria will be recorded. This will include presence of atrial fibrillation, peripheral vascular disease, scleroderma, an arteriovenous shunt, valvular heart disease. Details of concomitant illness of relevance to the analysis of the data will include known diagnosis of chronic arterial hypertension, chronic heart failure, ischaemic heart disease, chronic kidney disease, and diabetes mellitus.

### **2.11.2 Concomitant medication**

A record will be made of any patients who have taken an angiotensin-converting enzyme inhibitor, angiotensin II receptor blocker, calcium channel blocker or thiazide diuretic in the 24 hours immediately prior to surgery, as well as a record of any antibiotics the patient is being treated with.

## 2.12 Assessment of feasibility outcomes and improvements to trial protocol

### 2.12.1 Anaesthetic questionnaire

Following the final participation of a centre in the study, anaesthetists who took part in the study will be approached to fill out a questionnaire seeking to further understand their views on how the trial protocol can be improved, problems with the CNAP monitor and what they felt went well. This will be used to inform any future application for a full trial.

## 2.13 End of trial

The trial will be stopped when 30 patients have been recruited.

The trial will be stopped prematurely if:

- Mandated by the Research Ethics Committee (REC) or Health Research Authority (HRA)
- Mandated by the Medicines and Healthcare products Regulatory Agency (MHRA)
- Funding for the trial ceases

The Research Ethics Committee will be notified in writing within 90 days when the trial has been concluded or within 15 days if terminated early.

## 3. METHODS AND ASSESSMENTS

### 3.1 Schedule of delivery of intervention and data collection

*Describe the timescale over which the intervention is delivered, the times at which data will be collected and the type of data to be collected.*

*It is good to summarise the participant assessments in a table. This section should tally with what is being recorded in the CRF.*

**Table 1** Trial assessments

Visit	1	2	3	4
Visit Window	Pre-operative	Intra-operative	Post-operative D1-7	Follow up 30d
Verbal ( $\pm$ written consent)	✓			
Inclusion/exclusion criteria	✓			
Medical history	✓			
Intervention		✓		
Full written consent	(✓)		✓	
Adverse events		✓	✓	✓
Mortality			✓	✓

### 3.2 Laboratory assessments

There will be no laboratory assessments carried out specifically *by* the study. However, the study will record laboratory results of the serum creatinine concentration, serum troponin concentration, serum C-reactive Protein concentration, blood white cell count. These will be recorded from information available to the treating clinician only, and will not involve any research-specific samples.

### 3.3 Long term follow-up assessments

In hospital, and 30day mortality will be measured.

## 4. ADVERSE EVENT MANAGEMENT / PHARMACOVIGILANCE

### 4.1 Definitions

#### 4.1.1 Adverse Events (AE)

An Adverse Event (AE) is defined as any untoward medical occurrence in a participant and which does not necessarily have a causal relationship with this treatment/intervention.

iSTABILISE is a feasibility study that will look at the impact of continuous non-invasive blood pressure monitoring on intra- and post-operative patient outcomes. It is expected that patients undergoing hip fracture surgery may often suffer medical complications, up to and including death (see [32]). It follows that a large number of iSTABILISE trial participants will experience complications of surgery, which are completely unrelated to the trial intervention. Adverse events that are potentially related to study interventions will be recorded on study CRFs and if they fit the criteria for seriousness, then they will be reported as a SAE.

Adverse events which are expected, and do not need to be reported as such are not limited to, but include all of those measured as *outcomes*, as well as

- Constipation
- Pain
- Post-operative infections including sepsis
- Delirium
- Venous Thromboembolism
- Gastro-intestinal Bleeding
- Anaemia
- Electrolyte disturbances

#### 4.1.2 Serious Adverse Events (SAEs)

A Serious Adverse Event is an AE that fulfils one or more of the following criteria:

- Results in death
- Is immediately life-threatening
- Requires prolongation of existing hospitalisation
- Results in persistent or significant disability or incapacity
- Is a congenital abnormality or birth defect
- Is an important medical condition.

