**TRIAL SUMMARY**

Trial Title	Can continuous non-invasive monitoring improve stability of intraoperative blood pressure – A feasibility study in hip fracture surgery
ref. number	2019003AN
Clinical Phase	Phase III feasibility

Trial Design	Feasibility before-and-after trial	
Trial Participants	Adults undergoing surgery for repair of hip fracture	
Planned sample size	30 (15 control and 15 intervention patients)	
Treatment Duration	Intra-operative only.	
Follow-up Duration	In-hospital follow up to discharge, and mortality follow up to 30 days	
Planned Trial Period	From 01/06/2019-01/08/2019	
	Objectives	Outcome Measures
Primary	Demonstrate feasibility	Proportion of patients recruited who received the intervention, and completed follow up.
Secondary	Evaluate the incidence of intra-operative haemodynamic instability and post-operative adverse outcomes	Proportion of anaesthetic time with mean arterial pressure below set thresholds. Lowest recorded blood pressure. Amount of vasopressor and fluid given intraoperatively Post-operative incidence of acute kidney injury, myocardial infarction, stroke and death.

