## Reporting SAEs

All **SAEs** occurring from the time of **treatment allocation** until 30 days later must be recorded on the SAE Form and communicated to the Sponsor **within 24 hours** of the research staff becoming aware of the event.

For each **SAE** the following information will be collected:

- full details in medical terms and case description
- event duration (start and end dates, if applicable)
- action taken
- outcome
- seriousness criteria
- causality (i.e. relatedness to intervention), in the opinion of the investigator
- whether the event would be considered expected or unexpected.

Any change of condition or other follow-up information should be faxed to the Sponsor as soon as it is available or at least within 24 hours of the information becoming available. Events will be followed up until the event has resolved or a final outcome has been reached.

SAEs will be reported using the SAE form in the participant's CRF. The Principal Investigator in each centre must report any SAEs to the trial coordinating centre within 24 hours of them becoming aware of the event. The SAE form should be completed and emailed to the trial SAE Reporting email address. The trial coordinator will liaise with the investigator to compile all the necessary information. The trial coordinating centre is responsible for reporting any related and unexpected SAEs to the sponsor and REC within required timelines.

The causality and expectedness of SAEs (i.e. relationship to trial treatment) will be assessed by both the principal and chief investigator(s) on the SAE form.

Relationship to trial intervention	Description
Unrelated	There is no evidence of any causal relationship
Unlikely to be related	There is little evidence to suggest there is a causal relationship (e.g. the event did not occur within a reasonable time after administration of the trial intervention or device). There is another reasonable

	explanation for the event (e.g. the patient's clinical condition, other concomitant treatment).
Possible relationship	There is some evidence to suggest a causal relationship (e.g. because the event occurs within a reasonable time after administration of the trial intervention or device). However, the influence of other factors may have contributed to the event (e.g. the patient's clinical condition, other concomitant treatments).
Probable relationship	There is evidence to suggest a causal relationship and the influence of other factors is unlikely.

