### **5.1 Data collection and management**

The Case Report Forms (CRFs) will be developed to collect all required trial data. On completion, original CRFs will be sent to Heartlands Hospital MIDRU, and a copy retained at the study site within research site files. The maintenance and upkeep of research files will fall to site specific research team and site PI. These files will be routinely checked upon monitoring visits conducted by MIDRU staff as per monitoring plan.

Data up to hospital discharge, and information on survival at 30 days will be recorded by the site research staff, based on the visit schedule detailed in table one and all data will be collected within CRF and stored in the research site file. Any information that is relevant to the participant's clinical care will be recorded in both researcher site file and patient care records, as to allow for transparency between clinicians and researchers of the participants health.

Data will be entered on to the trial database by staff based at the study site. The data entry clerk will enter data on to the trial database as soon as possible after receipt as per data management plan. The CRF will be reviewed for missing data, conflicting data, and other apparent errors. Where necessary, a data query will be raised for resolution by the study site.

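### The seriousness criteria cover prolongation of a hospital stay but not a new admission, so a readmission within the 30-day SAE window is not serious in itself

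*Combined protocol and SAP*

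**What the plan says.** Section 4.1.2 opens with "A Serious Adverse Event is an AE that fulfils one or more of the following criteria" and lists six: death, immediate threat to life, "Requires prolongation of existing hospitalisation", lasting disability or incapacity, congenital abnormality, and "Is an important medical condition". The last is not defined. Neither a new admission nor a readmission appears.

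Under Reporting SAEs, all SAEs from treatment allocation "until 30 days later must be recorded on the SAE Form and communicated to the Sponsor", within 24 hours of staff becoming aware. The window does not end at discharge.

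Section 4.1.1 makes seriousness the gate. Potentially related adverse events go on the CRF, and "if they fit the criteria for seriousness, then they will be reported as a SAE". The same section exempts expected events from reporting: every trial outcome, plus an open-ended list that includes infection, venous thromboembolism, gastro-intestinal bleeding and delirium.

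The follow-up descriptions differ. The Trial Summary gives "In-hospital follow up to discharge, and mortality follow up to 30 days", and section 5.1 says "Data up to hospital discharge, and information on survival at 30 days will be recorded by the site research staff". Table 1 in section 3.1 ticks adverse events as well as mortality at the 30-day follow-up.

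**The concern.** A discharged patient has no current stay, so the hospital-care criterion cannot apply to that patient even though the reporting window is still open. Readmission is an obvious marker of non-fatal harm after discharge, yet nothing in the definition responds to it.

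What is at stake is how an event is classed and how fast it is escalated. Seriousness starts the 24-hour report to the sponsor. For related and unexpected events it also starts the Chief Investigator's immediate review and the sponsor's expedited report to the ethics committee (section 4.2). A related event classed as non-serious would be recorded as an AE without those steps. The study is also meant to inform a larger trial (sections 2.2.3 and 6.1), so the wording could be carried forward.

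**Working it through.** The documents give no figure on this point, so the check compares the sections. Take one event that is potentially related to the intervention and is not among the exempt events of section 4.1.1. It is treated successfully, does not threaten life and leaves no disability. Suppose it occurs either before discharge, lengthening the stay, or after discharge but inside the window, causing readmission.

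| Criterion in section 4.1.2 | Before discharge | After discharge |
|---|---|---|
| Death | no | no |
| Immediate threat to life | no | no |
| Prolongation of a current stay | **yes** | cannot apply |
| Lasting disability or incapacity | no | no |
| Congenital abnormality | not relevant | not relevant |
| Important medical condition | judgement | judgement |

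One criterion is enough. Before discharge the event is an SAE by an explicit rule. After discharge it is an SAE only through the undefined last criterion, and section 4.2 leaves seriousness to the Principal Investigator's medical judgement. The classification can therefore turn on the discharge date alone.

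Next, does any other text close the gap?

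- **Outcomes (sections 2.3.1 to 2.3.4).** Length of stay is the only hospital-use outcome. Readmission is not listed.
- **Post-discharge data (Trial Summary, sections 3.3 and 5.1).** Only survival or mortality at 30 days is described.
- **Table 1.** Adverse events are scheduled at 30 days, so a related event should be sought and recorded then. This does not make it serious.
- **Section 4.1.1.** The relatedness condition and the exemptions reduce the number of events that reach the seriousness question. They do not answer it for those that do.

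No section makes a new admission serious. The events affected are those that are potentially related, not exempt, arise after discharge, are neither fatal, life-threatening nor disabling, and are not judged medically important, yet lead to admission.

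**The case against.** The strongest reply is that the last criterion is there for such cases and that an experienced investigator would normally call a readmission medically important. Any one criterion suffices, so a readmission can be an SAE under the current text. That stands, and it rules out saying that readmissions are excluded from SAE reporting. But the criterion only permits reporting. It does not require it, and no guidance supports consistent use.

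A second reply is that the section 4.1.1 exemptions, rather than this bullet, decide most cases. Infection, thromboembolism, bleeding and all trial outcomes need not be reported as adverse events, and only potentially related events are directed to the forms. This also stands, and it limits what the bullet can be blamed for. It is itself unsettled, because Reporting SAEs speaks of all SAEs without repeating either restriction.

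Third, the intervention is the visibility of a non-invasive monitor, used only during surgery, in 15 of 30 patients, and the documents identify no delayed harm from it. That bears on how many events are likely, not on whether the definition fits its window.

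A reader might go further and infer that SAE counts in both cohorts will be too low, or that the definition largely fails after discharge. The documents support neither. Death, life threat, disability and medical importance all still apply after discharge, and nothing shows how investigators would use the last of these. Nor would the share of the 30 days that falls after discharge measure missed SAEs. No length of stay is given, and calendar days are not events.

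**Conclusion.** The gap is real but narrow. The definition names prolongation and omits new admission, while its own window can outlast discharge. A readmission is therefore not serious in itself, and a related, non-exempt event may be classed differently before and after discharge.

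The number of events cannot be calculated from the documents. It is probably small given 30 patients, a non-invasive monitor, the relatedness condition and the broad exemptions. The conclusion assumes only that some patients are discharged before the window closes. The feasibility endpoints, the intraoperative outcomes and the sample size are unaffected. The correction is worth making because it concerns safety reporting and costs little.

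**What to change.** 1. In section 4.1.2, widen the third bullet so that an event is serious if it requires hospitalisation, including readmission after discharge, or prolongs a current stay.
2. Add a readmission item to the CRF for the 30-day follow-up, where Table 1 already schedules adverse events. Amend the Trial Summary and section 5.1, which describe only survival or mortality after discharge, to agree with Table 1.
3. Reconcile section 4.1.1 with Reporting SAEs. State whether the exemptions and the relatedness condition apply to events that meet a seriousness criterion. Without this, the first change closes only part of the gap.

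The cost is one bullet, one CRF item at a contact already planned, some aligned wording and a few more SAE forms. Admissions to other hospitals may still be missed. Design and analysis do not change.

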## Reporting SAEs

All **SAEs** occurring from the time of **treatment allocation** until 30 days later must be recorded on the SAE Form and communicated to the Sponsor **within 24 hours** of the research staff becoming aware of the event.

For each **SAE** the following information will be collected:

- full details in medical terms and case description
- event duration (start and end dates, if applicable)
- action taken
- outcome
- seriousness criteria
- causality (i.e. relatedness to intervention), in the opinion of the investigator
- whether the event would be considered expected or unexpected.

Any change of condition or other follow-up information should be faxed to the Sponsor as soon as it is available or at least within 24 hours of the information becoming available. Events will be followed up until the event has resolved or a final outcome has been reached.

SAEs will be reported using the SAE form in the participant's CRF. The Principal Investigator in each centre must report any SAEs to the trial coordinating centre within 24 hours of them becoming aware of the event. The SAE form should be completed and emailed to the trial SAE Reporting email address. The trial coordinator will liaise with the investigator to compile all the necessary information. The trial coordinating centre is responsible for reporting any related and unexpected SAEs to the sponsor and REC within required timelines.

The causality and expectedness of SAEs (i.e. relationship to trial treatment) will be assessed by both the principal and chief investigator(s) on the SAE form.

Relationship to trial intervention	Description
Unrelated	There is no evidence of any causal relationship
Unlikely to be related	There is little evidence to suggest there is a causal relationship (e.g. the event did not occur within a reasonable time after administration of the trial intervention or device). There is another reasonable

	explanation for the event (e.g. the patient's clinical condition, other concomitant treatment).
Possible relationship	There is some evidence to suggest a causal relationship (e.g. because the event occurs within a reasonable time after administration of the trial intervention or device). However, the influence of other factors may have contributed to the event (e.g. the patient's clinical condition, other concomitant treatments).
Probable relationship	There is evidence to suggest a causal relationship and the influence of other factors is unlikely.
Definitely related	There is clear evidence to suggest a causal relationship and other possible contributing factors can be ruled out.

## 4.2 Responsibilities

### Principal Investigator (PI):

Checking for AEs when participants attend for treatment / follow-up.

1. Using medical judgement in assigning seriousness, causality and expectedness
2. Ensuring that all SAEs are recorded and reported to the Sponsor within 24 hours of becoming aware of the event and provide further follow-up information as soon as available. Ensuring that SAEs are chased with Sponsor if a record of receipt is not received within 2 working days of initial reporting.
3. Ensuring that AEs are recorded and reported to the Sponsor in line with the requirements of the protocol.

### Chief Investigator (CI) / delegate or independent clinical reviewer:

1. Clinical oversight of the safety of patients participating in the trial, including an ongoing review of the risk / benefit.
2. Using medical judgement in assigning seriousness, causality and expectedness of SAEs where it has not been possible to obtain local medical assessment.
3. Using medical judgement in assigning expectedness.
4. Immediate review of all related and unexpected SAEs
5. Review of specific SAEs in accordance with the trial risk assessment and protocol as detailed in the Trial Monitoring Plan.
6. Production and submission of annual reports to the relevant REC.

### Sponsor:

1. Central data collection and verification of AEs, and SAEs, according to the trial protocol.
2. Reporting safety information to the CI, delegate or independent clinical reviewer for the ongoing assessment of the risk / benefit according to the Trial Monitoring Plan.
3. Reporting safety information to the independent oversight committees identified for the trial (Data Monitoring Committee (DMC) and / or Trial Steering Committee (TSC)) according to the Trial Monitoring Plan.
4. Expedited reporting of related and unexpected SAEs to the REC within required timelines.

5. Notifying Investigators of related and unexpected SAEs that occur within the trial.

### **4.3 Notification of deaths**

Deaths are expected in this population and will be reported to the TMG on a monthly basis and to the TOC.

### **4.4 Reporting urgent safety measures**

If any urgent safety measures are taken the CI/Sponsor shall immediately and in any event no later than 3 days from the date the measures are taken, give written notice to the relevant REC of the measures taken and the circumstances giving rise to those measures.

## **5. DATA MANAGEMENT**

Personal data collected during the trial will be handled and stored in accordance with the 1998 Data Protection Act. Following recruitment, participants will be identified using a unique identification number and initials only to maintain anonymisation of research data.

All data will be handled as per data management plan, current data protection legislation.

### **5.1 Data collection and management**

The Case Report Forms (CRFs) will be developed to collect all required trial data. On completion, original CRFs will be sent to Heartlands Hospital MIDRU, and a copy retained at the study site within research site files. The maintenance and upkeep of research files will fall to site specific research team and site PI. These files will be routinely checked upon monitoring visits conducted by MIDRU staff as per monitoring plan.

Data up to hospital discharge, and information on survival at 30 days will be recorded by the site research staff, based on the visit schedule detailed in table one and all data will be collected within CRF and stored in the research site file. Any information that is relevant to the participant's clinical care will be recorded in both researcher site file and patient care records, as to allow for transparency between clinicians and researchers of the participants health.

Data will be entered on to the trial database by staff based at the study site. The data entry clerk will enter data on to the trial database as soon as possible after receipt as per data management plan. The CRF will be reviewed for missing data, conflicting data, and other apparent errors. Where necessary, a data query will be raised for resolution by the study site.

